11.6 Recording Adverse Events

All AEs (including SAEs) are to be accurately recorded on the Adverse Event/Serious Adverse Event page(s) of the CRF. The Investigator will carefully evaluate the seriousness, severity, duration, and causality of AEs and document the following on the CRF:

- Severity. In most cases the NCI-CTCAE v4.0 criteria will preferably be used to grade severity; however, if an AE is not listed in the CTCAE, the following grading scale may be used: Mild (Grade 1), Moderate (Grade 2), Severe (Grade 3), Life-Threatening (Grade 4), or Fatal (Grade 5).
- Duration of the event. The date of onset, duration of the event, method used to treat the AE, and the outcome of the AE should be noted.
- Relationship to study drug: Unrelated, Possibly Related, Probably Related, or Related.

11.7 Determining Relationship of Adverse Events to Study Drug

The following definitions adapted from [Karch \(1975\)](#) will be used to determine the relationship of AEs to study drug.

11.7.1 Unrelated

Category applies to adverse events which are clearly felt to be due to extraneous causes (disease, environment, etc.) that are unrelated to the study drug.

11.7.2 Possibly Related

The relationship to the study drug can be considered possible if (must have first 2):

- It follows a reasonable temporal sequence from administration of the drug.
- It could readily have been a result of the subject's clinical state, environmental or toxic factors, or other modes of therapy administered to the subject.
- It follows a known response pattern to the suspected drug.

11.7.3 Probably Related

The relationship to the study drug can be considered probable if (must have first 3):

- It follows a reasonable temporal sequence from administration of the drug.
- It could not be reasonably explained by the known characteristics of the subject's clinical state, environmental or toxic factors, or other modes of therapy administered to the subject.
- It disappears or decreases upon cessation of drug or reduction in dose.*
- It follows a known response pattern to the suspected drug.

**There are exceptions when an AE does not disappear upon discontinuation of the drug, yet drug relatedness clearly exists, e.g., 1) tardive dyskinesia; 2) fixed drug eruptions.*

11.7.4 Related

The relationship to the study drug can be considered related if (must have first 3):

- It follows a reasonable temporal sequence from administration of the drug or drug levels have been established in body fluids or tissues.
- It could not be reasonably explained by the known characteristics of the subject's clinical state, environmental or toxic factors, or other modes of therapy administered to the subject.
- It disappears or decreases upon cessation of drug or reduction on dose and appears upon rechallenge.*
- It follows a known response pattern to the suspected drug.

**There are exceptions when an AE does not disappear upon discontinuation of the drug, yet drug relatedness clearly exists, e.g., 1) tardive dyskinesia; 2) fixed drug eruptions.*

11.8 Reporting Deaths and Other Serious Adverse Events

11.8.1 Events to Be Reported and Timeframe

Any death or other serious adverse event experienced by the subject during treatment or within 30 days of receiving study drug, regardless of relationship to study drug, or any death that occurs more than 30 days after receiving study drug and is believed to be study drug-related, must be promptly reported to the Sponsor (within 24 hours of the Investigator becoming aware of the event) by telephone, telefax, or e-mail transmission.

11.8.2 Events Excluded from Expedited Reporting to FDA

The Sponsor does not plan to report several types of individual SAEs to FDA in an expedited manner because they are known consequences of the underlying disease and/or anticipated to occur in the trial population at some frequency, independent of drug exposure. These include:

- Progression of the underlying malignancy
- Death due to the underlying malignancy
- Elective hospitalization for transfusion or diagnostic procedure
- Previously scheduled elective surgery

These events will be reported to FDA/other regulatory authorities and all participating Investigators as an IND safety report only if there is evidence, based on an aggregate analysis, to suggest a causal relationship between the study drug and the adverse event.

11.8.3 Governing Regulatory Requirements

Compliance with this request for prompt reporting is essential in that the Sponsor is responsible for informing the US Food and Drug Administration (FDA) and other regulatory authorities as well as all other participating Investigators of the event.

Under FDA ruling (US Code of Federal Regulations, Title 21 CFR Part 312.32) and the ICH Guidelines for Clinical Safety Data Management Definitions and Standards for Expedited Reporting, the Sponsor is required to submit written documentation, in the form of an IND Safety Report, on the following:

- SUSARs.
- Unexpected fatal or life-threatening suspected adverse reactions.
- Findings from other studies that suggest a significant risk to humans exposed to drug.
- Findings from animal or in vitro testing that suggest a significant risk to humans exposed to drug.
- Increased rate of occurrence of serious suspected adverse reactions from what is reported in the Investigator Brochure or the protocol.

Written submission must be made by the Sponsor to the FDA/other regulatory authorities (and by the Investigator to the IRB/EC) as soon as possible, and in no event later than **15 calendar days** after the Sponsor determines that the information qualifies for reporting. The Sponsor shall also inform all Investigators.

In addition, the Sponsor is further required to report, by either telephone or facsimile transmission or in writing to the FDA/other regulatory authorities the occurrence of any unexpected fatal or life-threatening event associated with the use of the drug (SUSARs) no later than **7 calendar days** after notification of the event, followed by a written report **no later than 15 calendar days** after the initial report receipt date. The Sponsor shall also inform all Investigators.

The Sponsor will provide expedited reports of the following SUSARs to Investigators for reporting to their IRB/EC:

- SUSARs that have arisen in the clinical trial that was assessed by the IRB/EC.
- SUSARs that have arisen in other clinical trials of the same Sponsor and with the same medicinal product, and that could have consequences for the safety of the subjects involved in the clinical trial that was assessed by the IRB/EC.

Investigators are required to promptly report to the IRB/EC all unanticipated problems involving risk to human subjects, including adverse events that should be considered unanticipated problems (21 CFR 312.53(c)(1)(vii), 312.66, and 21 CFR 56.108(b)(1)).

11.8.4 Initial Information Provided by the Investigator

The Investigator must transmit sufficient initial information to the Sponsor (or designee) should an SAE report meet the criteria for completion of an IND Safety Report. As much of the following information about the subject and the event will be requested:

- Subject identification code, gender, and age or date of birth
- Underlying diagnosis and extent of disease
- Lot number and expiration date of study drug (if available)
- Dose, route, frequency, and duration of study drug administered
- Date of study drug administration
- Description of event, including date of onset and duration
- Date of death (if applicable)
- Intervention(s) required
- Concomitant therapy (including regimens and indications)
- Pertinent laboratory data/diagnostic study (including dates)
- Pertinent medical history
- Study drug status (dose interrupted, discontinued)
- Did event abate after interruption of study drug administration (if applicable)?
- Did event recur after study drug was reintroduced (if applicable)?
- Severity of the AE
- Relationship of the AE to study treatment
- Outcome of the AE

11.8.5 Follow-up Information

Follow-up data concerning the SAE (e.g., diagnostic test reports, physician's summaries, etc.) must also be submitted to the Sponsor as they become available, preferably by telefax or e-mail, as soon as they become available, and until the event resolves or stabilizes.

11.9 SAE and SUSAR Review and Potential Impact on Trial Conduct

The Investigator will review each SAE report and evaluate further the relationship of the SAE to study drug and to the subject's underlying disease.

Based on the Investigator's and Sponsor's assessment of causality of the adverse event and discussions with the Medical Monitor, a decision will be made by the Sponsor concerning the need for further action with respect to the future conduct of the trial. The primary consideration governing further action is whether new findings affect the safety of other subjects participating in the clinical trial. If the discovery of a new AE related to study drug raises concern over the safety of its continued administration to subjects, the Sponsor will take immediate steps to notify FDA, other regulatory authorities, and all Investigators participating in clinical trials with the study drug.

Further action required may include any of the following:

- Alteration of the existing research program by modification of the protocol.
- Discontinuation or suspension of the trial.
- Alteration of the informed consent process by modification of the existing consent form and informing current trial participants of new findings.
- Modification of previously identified expected suspected adverse reaction lists to include adverse events newly identified as study drug-related.

12.0 STATISTICAL METHODS AND PLANNED ANALYSES

12.1 General Considerations

This is a multicenter, randomized, double-blind, placebo-controlled trial in subjects with advanced HCC and CPB cirrhosis whose disease has progressed while taking 1 prior systemic drug therapy for HCC. The trial will evaluate the efficacy and safety of CF102 as compared to placebo. Subjects will be randomly assigned in a 2:1 ratio to treatment with oral doses of either CF102 25 mg or matching placebo administered BID for consecutive, 28-day cycles. Subjects will be evaluated regularly for safety including changes in laboratory parameters, vital signs, physical examination, ECOG PS, and ECG assessments compared to baseline findings. Treatment will continue until the subject experiences unacceptable drug-related intolerability. Subjects will return for a follow-up visit 28 days after completion of the last dose of study drug. Subjects who discontinue will be followed indefinitely for survival status.

The primary efficacy endpoint will be OS, defined as the number of days from first dose to death due to any cause. Secondary endpoints to be evaluated are TTP, PFS, OR consisting of CR or PR for subjects who enter the trial with measurable disease by RECIST v1.1, and DC which includes both subjects with OR as well as those with SD. Survival status will be assessed continuously. Tumor status will be assessed at the Pre-Study Visit and every 8 weeks thereafter (i.e., at the end of even-numbered cycles) by CT scan or MRI according to RECIST v1.1 ([Appendix A](#),

Eisenhauer, 2009 [as modified by Santoro 2013]). Liver Chemistry Tests, INR, and viral load will be presented as exploratory efficacy variables, as will WBC adenosine A₃ receptor expression. PK blood samples collected on Day 1 of Cycles 1 and 2 and trough samples collected on Days 8 and 15 of Cycle 1 will be used to generate a composite PK profile for subjects receiving CF102 treatment, and allow exploratory analysis of exposure-response for this trial.

12.2 Sample Size Determination

Approximately 78 subjects will be enrolled and randomized to either CF102 or placebo using a 2:1 randomization. The post-accrual treatment period was originally planned to continue until a total of 75 deaths have been recorded. Assuming a hazard ratio of 0.5, 75 events will provide 80% power for the logrank test at level 0.05 (two-sided). It is assumed that the 78 subjects will be enrolled in approximately 78 weeks and the trial will continue for a total of 104 weeks (SiZ: Logrank Test with Given Accrual Duration and Study Duration, Version 2.0, Cytel, Inc. 2011). The required number of deaths and the required number of subjects are reasonably stable with respect to the duration of accrual and length of the post-accrual follow-up period, being between 70 and 80, to have power of 80% for an assumed hazard rate of 0.5, especially for studies with a post-accrual follow-up period.

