4.2.2 Phase 1/2 Trial in Subjects with HCC (Study CF102-102HCC)

An open-label trial was conducted in 19 subjects with advanced unresectable HCC to evaluate the safety and PK profile of CF102 given orally (1, 5, and 25 mg BID) in 28-day cycles (Stemmer, 2013). Evaluation of the antitumor effects and the utilization of A₃AR as a biological predictive marker of response to CF102 were secondary objectives.

CF102 demonstrated good oral bioavailability and linear PK behavior in subjects with Child-Pugh A and B hepatic dysfunction. The best response by RECIST criteria was SD in 5/17 subjects (29.4%). Median overall survival (OS) was 8.2 months for all subjects, 8.3 months for subjects with no prior sorafenib use, and 7.2 months for subjects with prior sorafenib and for Child-Pugh class A hepatic dysfunction subjects. Median OS in Child-Pugh class B hepatic dysfunction subjects was 9.5 months.

These results are encouraging in light of the fact that 63% of the subject population had disease progression on sorafenib and that, for these subjects, CF102 treatment was second-line therapy.

The most common adverse events (all causalities combined) were decreased appetite (52.6%); fatigue (42.1%); abdominal pain, constipation, and diarrhea (31.6% each); ascites and pyrexia (26.3% each); and nausea, asthenia, back pain, and pain in extremity (21.1% each). CF102-related AEs included fatigue (26.3%), asthenia and decreased appetite (21.1% each), and pyrexia and constipation (15.8% each). Grade 3 drug-related AEs included: cerebral hemorrhage, headache, hyponatraemia, fatigue, asthenia, and back pain. One death (5.3%) due to cerebral hemorrhage was judged possibly related to CF102 by the Investigator. SAEs with fatal outcomes in 5 subjects were judged as not related to CF102.

CF102 had no adverse effect on routine measures of liver function over a 6-month period in 12 subjects treated for at least that duration. No dose-limiting toxicities were observed during the trial and the MTD was not reached.

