4.5.2 Potential Benefits

Previous experience has shown that the OS for Child-Pugh Class B patients with HCC is in the range of 3.5–5.5 months (Pinter, 2009; Pinter, 2011; Hollebecque, 2011). More importantly, data emerging from a number of recent trials have indicated that the median OS for patients with CPB and HCC who have failed treatment with sorafenib is generally no more than 2 months (Pinter, 2009; Wörms, 2009; Kim, 2011; Hollebecque, 2011; Abou-Alfa, 2011; Chiu, 2012; Køstner, 2013; Pressiani, 2013; Zugazagoitia, 2013).

Considering that Child-Pugh Class B patients with HCC have few available treatment options, and that these patients when treated with sorafenib generally have poor outcomes with very limited OS due to underlying liver dysfunction, CF102 may offer a therapeutic option for this sub-population of patients. CF102 has the further advantage of lacking, to date, any evidence of hepatotoxicity, making it highly suitable for use in patients with CPB cirrhosis.

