6.4 Duration of Trial

The subject accrual period is estimated to be approximately 102 weeks (~24 months) in duration. Each treatment cycle will be 28 days of daily dosing. Study drug treatment may continue until the subject experiences unacceptable drug-related intolerability ([Section 8.2](#)).

The post-accrual treatment period will continue until a total of 75 subjects have died.

Once the requisite number of events has occurred and the blind is opened for analysis of the trial results, any surviving subjects who remain on blinded drug will be offered the opportunity to continue dosing with open-label CF102 25 mg BID indefinitely, following the protocol-specified schedule of events ([Table 1–2](#)).

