7.0 SELECTION OF SUBJECTS

7.1 Inclusion Criteria

Subjects must meet all of the following inclusion criteria to be eligible for the trial:

1. Males and females at least 18 years of age.
2. Diagnosis of HCC:
 - For subjects without underlying cirrhosis at the time of diagnosis, diagnosis of HCC documented by cytology and/or histology.
 - For subjects with underlying cirrhosis at the time of diagnosis, diagnosis of HCC established according to the American Association for the Study of Liver Diseases Practice Guideline algorithm ([Appendix E](#)).
3. HCC is advanced, i.e., treatment-refractory or metastatic, and no standard therapies are expected to be curative.
4. Receipt of prior sorafenib therapy for at least 3 weeks and withdrawal from treatment due either to intolerability or to radiographic evidence of disease progression. If treatment was withdrawn due to intolerability manifested as a Grade 3 or 4 event by National Cancer Institute Common Toxicity Criteria for Adverse Events (CTCAE v4.0), less than 3 weeks of continuous prior administration prior to withdrawal is acceptable (see also Exclusion Criterion #3).
5. Prior sorafenib treatment was discontinued for at least 2 weeks prior to the Baseline Visit.
6. Eastern Cooperative Oncology Group (ECOG) performance status (PS) of ≤ 2 ([Appendix B](#)).

7. Cirrhosis classified as Child-Pugh Class B ([Appendix C](#)).
8. The following laboratory values must be documented ≤ 3 days prior to the first dose of study drug:
 - Absolute neutrophil count (ANC) $\geq 1.5 \times 10^9/L$
 - Platelet count $\geq 75 \times 10^9/L$
 - Serum creatinine ≤ 2.0 mg/dL
 - Aspartate aminotransferase (AST) and alanine aminotransferase (ALT) $\leq 5 \times$ the upper limit of normal (ULN)
 - Total bilirubin ≤ 3.0 mg/dL
 - Serum albumin ≥ 2.8 g/dL
 - Prothrombin time (PT) no greater than 6 seconds longer than control.
9. Life expectancy of ≥ 6 weeks.
10. For women of childbearing potential, negative serum pregnancy test result.
11. Provide written informed consent to participate.
12. Willing to comply with scheduled visits, treatment plans, laboratory assessments, and other trial-related procedures.

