7.6 Replacement of Subjects

No replacement of subjects is planned in this trial.

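### Protocol 12.2 pairs 75 deaths among about 78 unreplaced subjects with a 104-week trial, but the protocol's cited survival figures give about 52 to 72 deaths by then, and no fallback fixes when the primary analysis happens

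*Protocol*

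**What the plan says.** **Design inputs.** Protocol 12.2 randomizes about 78 subjects 2:1. "Assuming a hazard ratio of 0.5", it says that "75 events will provide 80% power for the logrank test at level 0.05 (two-sided"). The schedule behind this is that "78 subjects will be enrolled in approximately 78 weeks and the trial will continue for a total of 104 weeks". The section gives no survival median for either arm and no allowance for loss to follow-up. It adds that the required number of deaths and subjects stays between 70 and 80 over a range of durations.

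**Analysis trigger.** Protocol 6.4 says: "The post-accrual treatment period will continue until a total of 75 subjects have died". SAP 3.1 keeps the same rule in the present tense. Protocol 12.2 refers to it as what was planned at the outset and does not say what replaced it. SAP 2.2 says that enrolment itself runs until 75 deaths, which conflicts with a fixed sample of about 78.

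**Follow-up.** Protocol 7.6: "No replacement of subjects is planned in this trial". Protocol 7.4 and 11.2 provide indefinite survival follow-up after discontinuation. Protocol 7.5 lists loss of contact and withdrawn consent as ways of leaving the trial.

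**Survival figures.** Protocol 4.5.2 gives 3.5 to 5.5 months for Child-Pugh B patients with HCC. For those "who have failed treatment with sorafenib is generally no more than 2 months", which is this trial's setting, the figure is an upper bound. Protocol 4.2.2 reports, from a 19-subject open-label trial of CF102: "Median OS in Child-Pugh class B hepatic dysfunction subjects was 9.5 months". Entry requires "Life expectancy of ≥ 6 weeks" (Protocol 7.1).

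**The concern.** The trigger needs 75 of 78 subjects (96.2%) to have an observed death. The last subjects enter at about week 78, so at week 104 they have only 26 weeks of follow-up. Under a hazard ratio of 0.5, the larger arm has twice the placebo median. Whether 96% mortality is plausible by then depends on a survival assumption that 12.2 does not state.

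The timing of the primary overall survival analysis is at stake. If the trial were analysed at 104 weeks, the power would be below the stated figure over most of the cited range. If it waits for 75 deaths, it may wait far longer than the stated duration, or indefinitely if a few subjects are lost. The plan has no calendar fallback, so someone would have to choose a cut-off ad hoc.

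**Working it through.** **1. The plan's own figure.** Schoenfeld's formula with two-sided alpha 0.05, 80% power, HR 0.5 and 2:1 allocation:

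(1.960 + 0.842)² / [(2/3)(1/3)(ln 0.5)²] = 73.5, so 74 deaths.

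Power at 75 deaths is Φ(√(75 × 2/9) × ln 2 − 1.960) = Φ(0.870) = 80.8%. The protocol's 75 deaths for 80% power is therefore sound.

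**2. Expected deaths at week 104.** Inputs from the documents: 26 placebo and 52 CF102 subjects, accrual A = 78 weeks, total T = 104 weeks, HR 0.5. My assumptions: exponential survival, uniform accrual, no dropout, 1 month = 4.348 weeks.

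For an arm with median m months, λ = ln 2 / (4.348 m) per week. The expected proportion alive at T is

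[exp(−λ(T − A)) − exp(−λT)] / (λA).

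At a placebo median of 2 months (CF102 4 months):
- Placebo: λ = 0.0797, proportion alive 0.020, so 0.5 of 26 alive.
- CF102: λ = 0.0399, proportion alive 0.109, so 5.7 of 52 alive.
- Expected deaths: 78 − 0.5 − 5.7 = 71.8.

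The same calculation over the cited range, with power from the formula in step 1 at the expected death count:

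| Placebo / CF102 median (months) | Expected deaths at week 104 | Power if analysed then | Expected time of 75th death (weeks) |
|---|---|---|---|
| 2 / 4 | 71.8 | 79% | 121 |
| 3.5 / 7 | 62.4 | 73% | 171 |
| 4.75 / 9.5 | 55.4 | 68% | 215 |
| 5.5 / 11 | 51.8 | 65% | 242 |

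The last column is the T at which expected deaths equal 75, with A held at 78 weeks. The third row takes the 9.5 months reported for Child-Pugh B on CF102 and halves it for placebo under HR 0.5. In 40,000 simulated trials at 2/4 months, 12% reached 75 deaths by week 104.

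**3. What the 104 weeks would need.** Setting expected deaths to 75 at T = 104 and solving gives a placebo median of 1.44 months (CF102 2.9 months). That is 1.44 × 4.348 = 6.3 weeks.

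**4. Margin for loss.** 78 − 75 = 3. With exactly 78 subjects, a fourth permanent loss of vital status caps the count at 74. The documents give no loss rate. If each subject were lost independently (an assumption), the binomial chance of three or fewer losses is 93% at a 2% loss rate, 45% at 5% and 4% at 10%.

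**The case against.** The strongest reply is that the plan is event-driven. The 104 weeks is an assumption in 12.2, and 6.4 and SAP 3.1 set no calendar limit. An optimistic duration makes the trial longer without invalidating its power. This stands. A reader might infer that 75 deaths are required within 104 weeks, or that the 80% power is wrong. The documents support neither: power is tied to the event count and reproduces. The 65% to 79% figures apply only if the analysis is done at week 104, which no passage prescribes.

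Second, the population that matters is Child-Pugh B after sorafenib, and the 2 months is an upper bound for it. At that bound 71.8 deaths fall inside the protocol's band of 70 to 80, with 79% power, and a median of 1.4 months or less would deliver 75. This also stands, so it would be too strong to say that the schedule cannot work. But no passage states a median that short, and the protocol also cites longer survival.

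Third, a reader might push the shortfall down to about 44 deaths by combining the 102-week accrual of 6.4 and SAP 3.1 with the 104-week total of 12.2. No passage pairs those two figures. On the schedule in 12.2 the range is 52 to 72.

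Fourth, four survivors do not block the trigger. Under indefinite follow-up they delay it, and only permanent loss of vital status blocks it. The sample is also only approximately 78, and SAP 2.2 taken literally would let enrolment continue.

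**Conclusion.** The stated duration and the stated event count do not fit together over the survival figures the protocol cites. The shortfall at week 104 is about 3 deaths at a 2-month placebo median and about 23 at 5.5 months. Under the event-driven rule this becomes a 75th death expected about 17 to 138 weeks after week 104, before any loss to follow-up. These sizes rest on exponential survival, uniform accrual, HR 0.5 and no dropout. The survival input to the sponsor's software calculation is not shown.

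The more consequential gap is the trigger. It requires observed deaths in 96% of subjects, with no loss allowance and no calendar fallback. One section treats the rule as superseded while two others keep it. Following the plan could leave the primary overall survival analysis late, unreachable after four permanent losses among exactly 78 subjects, or timed ad hoc.

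**What to change.** In Protocol 6.4 and 12.2 and SAP 2.2 and 3.1:

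- State the assumed survival medians and the loss-to-follow-up allowance.
- Replace the 104-week duration with one consistent with them, or state the expected deaths and power at 104 weeks: for example about 72 deaths and 79% at 2/4 months, or about 62 deaths and 73% at 3.5/7 months.
- Set one analysis trigger, for example 75 deaths or a fixed time after the last subject's first dose, whichever comes first. Reconcile it with the past-tense wording in 12.2 and with the SAP 2.2 sentence on enrolment.
- Where unblinding has already happened, do not write a new trigger. Document the cut-off rule and death count actually used, and the power at that count. SAP 7.6.8 and 9 record decisions taken after unblinding, so this branch applies to the current SAP version.
- Reconcile the passages on unblinding and open-label entry: Protocol 6.1 and 6.4 refer to the requisite number of events, while 7.7 and 9.1 refer to approval of Amendment 5.

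The cost is wording, with no extra subjects. The downside is that the stated power may become slightly to moderately less favourable.
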